4.4. Type and Number of Subjects

Adult subjects with symptomatic and systemically active disease as well as evidence of glandular reserve function will be recruited. A screen failure rate of 25% is anticipated. This implies 94 subjects must be screened in order to randomize approximately 70 subjects into the trial.

The total number of subjects randomized may increase following sample size re-estimation up to a maximum of 120 recruited into the study. The sample size re-estimation will be conducted at the interim analysis.

In addition, if subjects prematurely discontinue the study, additional subjects may be randomized and assigned to the next treatment in the randomization schedule at the discretion of the Sponsor.

4.5. Design Justification

This is a randomized, double-blind (sponsor open), placebo-controlled trial. Stable, low dose steroids (≤ 10 mg prednisone or equivalent) and hydroxychloroquine will be permitted in all treatment arms. The use of pilocarpine and cevimeline (at stable doses) as well as symptomatic therapies (such as ophthalmic lubricants, chewing gum) may be used for symptom relief during the treatment and follow up phases but would be prohibited within a period of time prior to endpoint assessments (see Section 6.9.1 for details). Considering that there are no disease modifying treatments for Sjögren's syndrome and that approved therapies consist of symptomatic treatments, inclusion of a placebo-controlled arm is ethically justifiable – especially considering these subjects will be allowed to continue stable low doses of standard of care treatments (steroids, hydroxychloroquine and symptomatic topical therapies).

4.6. Dose Justification

Dose Selection:

The belimumab 200 mg SC weekly dose was selected because it delivers a substantial molar excess of belimumab above free BLyS levels in the blood, resulting in rapid suppression of BLyS levels and is understood to be equivalent (by area under the curve, AUC) to the belimumab 10 mg/kg IV dose which has been shown to be safe and effective in patients with active SLE. A Phase III study with 200 mg belimumab administered SC weekly in SLE patients is currently ongoing. The double blind phase of this study was recently completed; the belimumab 200 mg SC weekly dose plus standard of care significantly improved SLE Response Index (SRI) and decreased time to severe flare compared with placebo plus standard of care. Furthermore, safety findings with belimumab plus standard of care were similar to that of placebo plus standard of care [Stohl, 2017]. In addition, a completed belimumab trial in patients with Sjögren's syndrome [BELISS study; Mariette, 2015] used the 10 mg/kg IV dose without unexpected adverse events.

The rituximab 1,000 mg IV dose (x2, 2 weeks apart) was selected because it causes rapid depletion of peripheral B cells to below the lower limit of quantification. Also, this regimen is the approved treatment course for patients with rheumatoid arthritis (RA). In addition, published trials of rituximab in patients with Sjögren's syndrome have used this regimen.

Dose Duration and Selection of Key Time Points:

In the co-administration therapy arm, rituximab treatment will commence at Week 8, two months after the start of belimumab. This will provide an opportunity to observe the anticipated increase in the memory B cell population in peripheral blood (mobilization endpoint) expected with belimumab and to determine whether greater increases in peripheral B cells correlate with greater efficacy for individual subjects in the co-administration therapy arm.

Following the last dose of rituximab therapy (which will be at Week 10 for the co-administration arm), B cell levels are predicted to remain suppressed below the level of quantification for at least 14 weeks [Emery, 2006; Meijer, 2010]. Therefore, Week 24 is a time point at which both anti-CD 20 and anti-BLyS pharmacodynamic effects are maximal, and was selected as the time point for primary efficacy comparison.

In the co-administration therapy arm, continuing belimumab treatment to Week 24 provides an opportunity to assess peripheral B cell reconstitution in the presence of prolonged BLyS suppression.

The Week 52 assessment provides an opportunity to determine whether treatment effects achieved at Week 24 in the co-administration therapy group can be maintained or improved after a drug-free follow up period (persistence of effect after treatment discontinuation) and to evaluate the effects of chronic (52 week) belimumab treatment on clinical, functional and mechanistic endpoints.

The primary efficacy comparison for this study at Week 24 will be between the co-administration therapy arm and the placebo arm.

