4.2. Treatment Arms and Duration

Approximately 70 subjects will be recruited into the study initially. Withdrawals may be replaced. At Day 0, subjects will be randomized 1:2:2:2 to one of the four treatment arms below.

1. Placebo Arm: Approximately 10 subjects will receive belimumab placebo weekly subcutaneous injections to Week 52 and rituximab placebo infusions at Weeks 8 and 10.
2. Belimumab Monotherapy Arm: Approximately 20 subjects will receive 200 mg weekly subcutaneous injections of belimumab to Week 52 and placebo rituximab infusions at Weeks 8 and 10.
3. Co-administration Therapy Arm: Approximately 20 subjects will receive belimumab 200 mg SC weekly for 24 weeks followed by weekly placebo belimumab injections to Week 52 with rituximab 1,000 mg intravenously at Weeks 8 and 10.
4. Rituximab Monotherapy Arm: Approximately 20 subjects will receive 1,000 mg IV rituximab infusions at Weeks 8 and 10 and weekly subcutaneous injections of placebo belimumab to Week 52.

The subjects will be stratified based on their baseline disease activity severity [ESSDAI 5-12 (moderate) vs. ESSDAI >12 (severe)] ensuring that within each disease severity there is an allocation across all treatment groups.

The total number of subjects recruited will be determined through an ongoing review of the data and sample size re-estimation. Following interim analysis, a number of actions could be taken: the study may continue as planned; one or more treatment arms may be dropped; the number of subjects in some or all treatment arms may be increased following sample size re-estimation, up to a maximum of 120 total subjects in the study where up to a maximum of 25, 45, 30 and 20 will be randomized to placebo, belimumab monotherapy, co-administration therapy and rituximab monotherapy respectively. The randomization ratio will vary dependent on the number of treatment arms continuing following the interim analysis.

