9. STATISTICAL CONSIDERATIONS AND DATA ANALYSES

9.1. Hypotheses and Treatment Comparisons

The primary objective of the study is to investigate the safety and tolerability of the co-administration of belimumab with rituximab and belimumab monotherapy. No formal statistical comparisons will be conducted to assess this objective.

Secondary efficacy and mechanistic endpoints will be investigated. The following exploratory comparisons may be conducted:

- Co-administration belimumab/rituximab treatment arm vs. Placebo arm
- Co-administration belimumab/rituximab treatment arm vs. Rituximab monotherapy arm
- Co-administration belimumab/rituximab treatment arm vs. Belimumab monotherapy arm
- Belimumab monotherapy arm vs. Placebo arm
- Belimumab monotherapy arm vs. Rituximab monotherapy arm

If deemed appropriate, these exploratory comparisons will be made investigating ESSDAI, stimulated salivary flow, oral dryness numeric response scale and a subset of salivary gland and plasma B cell parameters. Full details will be included in the RAP.

For all other parameters, no formal statistical comparisons will be made, although trends over time will be investigated across all treatment arms.

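### The mobilization-to-efficacy link is framed in the co-administration arm alone, and the listed contrasts do not pool arms that are treated identically until the Week 8 infusion

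*Protocol*

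**What the plan says.** Protocol Section 4.6 gives the reasons for the eight-week belimumab lead-in in the co-administration arm. One is to "observe the anticipated increase in the memory B cell population in peripheral blood (mobilization endpoint) expected with belimumab". Another is to "determine whether greater increases in peripheral B cells correlate with greater efficacy for individual subjects in the co-administration therapy arm". The second clause names one arm; the first does not.

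Section 4.2 sets the design: "Approximately 70 subjects will be recruited into the study initially", and "At Day 0, subjects will be randomized 1:2:2:2 to one of the four treatment arms below". The belimumab arm receives "200 mg weekly subcutaneous injections of belimumab to Week 52 and placebo rituximab infusions at Weeks 8 and 10". For placebo, "Approximately 10 subjects will receive belimumab placebo weekly subcutaneous injections to Week 52 and rituximab placebo infusions at Weeks 8 and 10".

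Section 9.1 states "The following exploratory comparisons may be conducted" and lists five, each setting one arm against one other. Section 9.4.3 applies those comparisons non-parametrically to some salivary gland histology measures and to B-cell quantification in plasma. It also leaves room for further exploratory work on how endpoints relate. Pooling of arms is not mentioned anywhere.

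**The concern.** The biology behind the lead-in (Section 2.2) is that belimumab moves tissue B cells into the blood, where anti-CD20 treatment can then deplete them. Two features of the plan serve that question poorly.

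First, mobilization is complete before any infusion, and up to that moment there are in effect two treatment groups, not four. Single-arm pairs use only part of the subjects who inform the contrast.

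Second, a correlation inside the co-administration arm has two readings: mobilized cells were then depleted by rituximab, or subjects who respond to belimumab do better whatever follows. The belimumab arm has the same lead-in and no rituximab, so it is the randomised comparator that could separate the two. Section 4.1 makes the mechanistic difference between monotherapy and co-administration a design aim, and a one-arm correlation does not address it.

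**Working it through.** **Plan figures.** The protocol gives no precision figure for mobilization or for the correlation. The only figures to reproduce are the arm sizes: 70/7 = 10 per unit of the 1:2:2:2 ratio, so 10 / 20 / 20 / 20, as Section 4.2 states.

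**Step 1: treatment before the first infusion (Section 4.2).**

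| Arm | n | Weekly injection to Week 8 |
|---|---|---|
| Belimumab | 20 | belimumab 200 mg |
| Co-administration | 20 | belimumab 200 mg |
| Rituximab | 20 | placebo |
| Placebo | 10 | placebo |

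Pooling identical pairs gives 20 + 20 = 40 belimumab-treated v 20 + 10 = 30 not.

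**Step 2: information on the mean Week 8 change.** Assume equal SD in all arms and work in SD units: I = 1/(1/n1 + 1/n2), SE = 1/√I, loss = 1 − I/I(pooled).

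| Contrast | n | I | SE | Loss v pooled |
|---|---|---|---|---|
| Co-administration v placebo | 20 v 10 | 6.67 | 0.387 | 61% |
| Co-administration v rituximab | 20 v 20 | 10.0 | 0.316 | 42% |
| Co-administration v both placebo-injection arms (not listed) | 20 v 30 | 12.0 | 0.289 | 30% |
| Pooled | 40 v 30 | 17.14 | 0.242 | – |

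Belimumab v placebo and belimumab v rituximab, also listed in Section 9.1, have the same sizes as the first two rows. At two-sided 5% and 80% power, the detectable difference (2.80 × SE) is 1.09 SD for 20 v 10 and 0.68 SD pooled.

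**Step 3: the post-interim caps (25 placebo, 45 belimumab, 30 co-administration, 20 rituximab).** Pooled is 75 v 45, I = 28.1. Co-administration v placebo (30 v 25) gives 13.6, a loss of 52%. Co-administration v rituximab (30 v 20) gives 12.0, a loss of 57%. The best listed contrast is then belimumab v placebo: 1/(1/45 + 1/25) = 16.1, a loss of 1 − 16.1/28.1 = 43%.

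**Step 4: correlation in one arm of 20.** On the Fisher z scale SE = 1/√17 = 0.243. Significance needs |r| of at least tanh(1.96 × 0.243) = 0.44. Power of 80% needs r of about tanh(2.80 × 0.243) = 0.59.

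**Step 5: can the two belimumab-treated arms be pooled for the correlation?** No. The Time and Events Table (Section 7.1) schedules ESSDAI, salivary flow and oral dryness at screening and then first at Week 12, after both infusions. By then the two arms have had different treatment. They can be compared, not merged.

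**Step 6: precision of the comparison, 20 v 20.** SE of the difference in Fisher z = √(1/17 + 1/17) = 0.343. Power of 80% needs a difference of 2.80 × 0.343 = 0.96, for example r = 0 in one arm and about 0.74 in the other.

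**The case against.** The Section 4.6 sentence is design rationale, not an analysis specification, and exploratory detail is deferred to the Reporting and Analysis Plan, which is not among the documents. That stands, and it limits the weight of the point. It does not remove it: the correlation clause names an arm, and Section 9.1 fixes the form of the contrasts. An analysis plan that followed both literally would contain neither the pooled contrast nor the comparator.

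A reader might infer that mobilization is read in one arm only, with no control and with data discarded. The documents do not support that. B-cell subsets are an exploratory endpoint without arm restriction (Sections 3 and 7.6.1.2), and leukocyte populations are scheduled at Day 0 and Weeks 1, 4 and 8 for everyone (Section 7.1). Section 9.1 has trends examined across all arms, and its list covers every pairing of a belimumab-treated arm with a placebo-injection arm. A reader might also take the loss to be over half in general. It is 30% to 61% at the initial sizes, depending on the reference.

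Limiting the correlation to co-administration subjects is partly deliberate, since only they and the rituximab arm are depleted and only they had the belimumab lead-in. But the hypothesis is about what rituximab adds, and that needs the arm without it.

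Finally, the slope difference is less precise than the single-arm correlation, by a factor of √2. That is true. It is still the quantity that answers the question, provided it is reported as an estimate and not relied on as a test.

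**Conclusion.** The point holds as an improvement to an exploratory analysis. Not pooling up to the Week 8 infusion costs 42% of the information against the best listed contrast and 61% against co-administration v placebo at the initial sizes. These figures assume equal SD, complete data and a comparison of means; the planned B-cell analyses are non-parametric, so they are a guide to relative size. The one-arm correlation cannot distinguish a rituximab-specific link from a prognostic one.

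The point does not extend to a claim that mobilization lacks controls, nor to a single correlation in 40 subjects. The study is stated not to be powered for pre-defined differences, and no primary or secondary conclusion depends on this.

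**What to change.** Add one or two sentences to Sections 4.6 and 9.1 and carry them into the Reporting and Analysis Plan:

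- For samples taken before the Week 8 infusion, estimate mobilization as belimumab-treated (belimumab plus co-administration) v not (rituximab plus placebo), stratified by the randomised ESSDAI stratum. If allocation changes or an arm is dropped after the interim analysis, stratify by randomisation stage too; otherwise pooling mixes periods with different allocation.
- Fit the relation of mobilization to later efficacy separately in the belimumab and co-administration arms. Report the between-arm difference in slope with its 95% CI, and state that precision is low at about 20 v 20.
- Mark the Week 8 leukocyte sample as pre-infusion. In the Time and Events Table, the Day 0 leukocyte sample and the Week 8 rituximab immunogenicity sample carry the pre-dose footnote, but the Week 8 leukocyte sample does not.

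The cost is wording only: the samples, visits and subjects stay the same.

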There are no clinical trial data for the co-administration of belimumab with rituximab; however, the following data were reviewed and no new safety risks beyond what would be expected for either agent alone was suggested from the very limited data available from patients (n=39) who may have had overlapping exposures to belimumab and rituximab:

- The GSK Safety Database of adverse events from clinical trials and post-marketing experience
- An insurance claims database (SafetyWorks)
- In-stream, blinded data from an ongoing GSK study of belimumab in subjects with vasculitis who were induced with high dose corticosteroids and either rituximab or cyclophosphamide.

Given that the experience of co-administered anti-CD20 and anti-BLyS to date is very limited, coupled with the introduction of dual biologic therapy in this new indication of pSS, robust safety monitoring and stopping rules are being implemented to safeguard subject safety. The key risk assessment and mitigation strategy for this protocol is outlined in Section [4.7.1](#).

4.7.1. Risk Assessment for Dual Biologics in pSS

Potential Risk of Clinical Significance	Summary of Data/Rationale for Risk	Mitigation Strategy
Investigational Product (IP) [belimumab (GSK1550188) & rituximab]		
Infections: Prolonged B-cell suppression and more complete B-cell depletion expected; potential for more profound hypogammaglobulinemia with increased risk for serious infections including opportunistic infections (OIs), PML, and HBV re-activation.	
Rituximab: The rate of serious infections with rituximab in the RA population is 4/100 per year.
 
Reactivation of hepatitis B has also been very rarely reported in RA patients receiving rituximab.
 
Late onset neutropenia occurs rarely in patients treated with rituximab.
 
Belimumab: The rate for belimumab in SLE is 5% of subjects receiving either belimumab or placebo.
 
Belimumab and Rituximab: Infections are expected events for both belimumab and rituximab.
 
Cases of PML have been very rarely reported, including fatal events, for both rituximab and belimumab in autoimmune diseases.
 
Dual Belimumab and Rituximab: There is pre-clinical evidence for prolonged B-cell suppression and more complete B-cell depletion as well as effect on IgG1+ plasma cells in the long-lived bone marrow niche thought to be less sensitive
	
Exclusions based on significant infection history, serologic evidence of past or present HBV or HCV infection; IgG < 550 mg / dL, IgA deficiency, neutrophils <1.5X10⁹/L.
 
A PML management plan including neurologic questionnaire and patient alert card.
 
Individual subject's treatment will be discontinued for (a) life-threatening infection; (b) IgG <400mg/dL (or <550mg/dL if associated with a serious infection); (c) neutrophils < 1X10⁹/L
 
Subjects will be monitored for up to 2 years or until B-cells return to LLN and monitored for late onset neutropenia at 6 months post-rituximab.

Potential Risk of Clinical Significance	Summary of Data/Rationale for Risk	Mitigation Strategy
	
to immunotherapy [Lin, 2015] with dual B-cell immunotherapy. Assessment of the translatability of the IgG reductions to humans is difficult to make due to species differences in B-cell biology and different treatments; however, the mouse data raises the hypothetical risk that immunoglobulin levels may reduce more with co-administration treatment.
	

Systemic Infusion / Injection Reactions, Hypersensitivity Reactions and Immunogenicity
 
There is a potential risk for increased ADA due to cross reactivity which could lead to increased frequency of hypersensitivity reactions, particularly of the delayed type.
 
Serum Sickness: The incidence of serum sickness associated with rituximab is higher in autoimmune indications and likely greater in Sjögren's Syndrome vs. RA [Meijer, 2010].
	
Rituximab: The incidence of serum sickness associated with rituximab in pSS studies has ranged from 6-38% [Carubbi, 2014].
 
Belimumab and Rituximab: Administration of belimumab and rituximab may result in infusion and hypersensitivity reactions, which can be severe and can be fatal. Delay in the onset of serious hypersensitivity reactions can occur. Both rituximab and belimumab have been associated with delayed type non-acute HSR/serum sickness, although no relationship to ADA has been established.
 
Dual Belimumab and Rituximab: Incidences of hypersensitivity and infusion reactions have been noted to be higher with co-administration vs.
	
ADA will be monitored with collection at baseline, Weeks 8, 24, and 52
 
A pre-medication regimen will be given before each rituximab/rituximab placebo infusion: methylprednisolone 100 mg IV, an oral antihistamine and analgesic.
 
Patients will be given an alert card for HSR and delayed HSR/serum sickness.

Potential Risk of Clinical Significance	Summary of Data/Rationale for Risk	Mitigation Strategy
	mono-biologic therapy but no association with ADA has been established [Weinblatt, 2006].	
Malignancy There is an increased risk of B-cell lymphoma in pSS. There is a theoretical increased risk of malignancy with combination immunosuppressive mechanisms; however, the potential synergistic effect of rituximab/belimumab would be assumed to result in a prolonged b-cell depletion that would not be dissimilar to repeat doses of rituximab.	Belimumab and Rituximab: Immunomodulatory drugs like rituximab and belimumab may increase the risk of malignancy. To date, no causal relationship to belimumab or rituximab to malignancy, including B-cell lymphoma, has been detected with either agent, both of which have been administered long term and in combination with other immunosuppressants of various mechanisms.	Subjects with a history of malignancy in the 5 yrs prior to randomization will be excluded (see Section 5.2, criterion #4).
Interaction with Vaccinations There is a risk of reduced antibody titers with mono and dual B cell immunotherapy. The potential synergistic effect of rituximab and belimumab may result in a prolonged B-cell depletion that should have a similar impact on vaccine response as administering repeated doses of rituximab.	
Rituximab: Median antibody titers (tetanus, diphtheria, pneumococcus) at Week 32 were reduced from baseline in atacicept but not placebo-treated patients who had been previously treated with rituximab. However, these values recovered close to baseline by Week 16 of the follow-up, there were few shifts to below protective titres, and no between-group differences with respect to the frequency of shifts.
 
Belimumab: the efficacy of concurrent vaccination in patients receiving belimumab is not known;
	
Live vaccination is prohibited from 30 days prior to Day 0 until the end of the general follow up period or IFU, if appropriate.
 
Subjects' vaccination status should be assessed and current immunization guidelines followed; all necessary vaccinations should be administered if possible no later than 30 days prior to Day 0.

Potential Risk of Clinical Significance	Summary of Data/Rationale for Risk	Mitigation Strategy
	
however, in the belimumab vaccination trial (study 115470, see GSK Clinical Study Register at www.gsk-clinicalstudyregister.com), evaluation of the impact of belimumab treatment on response to on-treatment vaccination with 23-valent pneumococcal vaccine revealed that immune responses to the different serotypes were similar in SLE patients receiving belimumab compared with those not receiving treatment at the time of vaccination.
	

Psychiatric Events
 
There is a potential risk of psychiatric events with belimumab and rituximab.
	
Rituximab: Depression and anxiety were common adverse events in rituximab RA trials.
 
Belimumab: There have been reports of depression and suicidality in patients receiving belimumab. A causal relationship to belimumab has not been established.
	
Subjects who, in the investigator's opinion, pose a significant suicide risk will be excluded.
 
The C-SSRS will be completed at each visit during which the subject may potentially be exposed to belimumab.
 
Subjects will be monitored closely for signs and symptoms of psychiatric illness including depression and suicidal ideation.
 
Subjects displaying such signs and symptoms will be treated appropriately and referred as necessary to specialty psychiatric care.

Potential Risk of Clinical Significance	Summary of Data/Rationale for Risk	Mitigation Strategy
Cardiac disorders	
Rituximab: Angina pectoris, cardiac arrhythmias such as atrial flutter and fibrillation, heart failure and/or myocardial infarction have occurred in patients treated with rituximab. There is no data on the safety of rituximab in patients with moderate to severe heart failure or severe, uncontrolled CV disease.
 
Belimumab and Rituximab: Hypotension may accompany infusion/post-injection systemic reactions with both rituximab and belimumab.
	
Exclude subjects with severe heart failure (New York Heart Association, Class IV) or other severe, uncontrolled cardiac disease.
 
Closely monitor any patients with cardiac history or those who have experienced prior cardiopulmonary adverse reactions during administration of rituximab/rituximab placebo. Consider withholding anti-hypertensive medications 12 hours prior to rituximab/rituximab placebo infusion.

Skin reactions	
Rituximab: Severe skin reactions such as Toxic Epidermal Necrolysis and Stevens-Johnson syndrome; some with fatal outcome, have been reported with rituximab.
	
Permanently discontinue treatment in the case of such an event with suspected relationship to treatment.

Posterior Reversible Encephalopathy Syndrome (PRES)	
Rituximab: Cases of PRES / reversible posterior leukoencephalopathy syndrome (RPLS) have been reported. Signs and symptoms included visual disturbance, headache, seizures and altered mental status, with or without associated hypertension. A diagnosis of PRES/RPLS
	
Medical monitor will be notified of any new neurologic symptoms (see Section 5.4.3). Medical monitor and investigator will consider the possibility of PRES in differential diagnosis.

Potential Risk of Clinical Significance	Summary of Data/Rationale for Risk	Mitigation Strategy
	requires confirmation by brain imaging. The reported cases had recognized risk factors for PRES/RPLS, including the patients' underlying disease, hypertension, immunosuppressive therapy and/or chemotherapy.	
Study Procedures		
Salivary gland Biopsy This procedure is associated with (a low) incidence of complications including bleeding and hematoma formation.	The reported incidence of bleeding and hematoma were 7.5% and 2.7%, respectively in a large case series [Santiago , 2012].	Subjects will be instructed to stop anticoagulant therapy (i.e., aspirin, NSAIDs, warfarin) prior to the procedure. Also, the biopsy will be performed by qualified physicians, surgeons or dentists and the personnel performing the biopsy will be required to undergo study-specific training in the performance of this procedure.

